4.2 STUDY ENDPOINTS

4.2.1 PRIMARY ENDPOINT

Symptomatic kidney stone recurrence. A symptomatic stone will be defined as any of the following:

1. Stone passage observed and/or captured by the study participant
2. Procedural intervention for symptomatic stone
3. Any procedural intervention for removal of asymptomatic renal or ureteral stone (See section 10.4.2 for analytic details)

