5 STUDY ENROLLMENT AND WITHDRAWAL

5.1 PARTICIPANT INCLUSION CRITERIA

1. Aged ≥ 12 years
2. At least 1 symptomatic stone event (passage or procedural intervention) within 3 years prior to enrollment or a symptomatic stone event within 5 years if the patient also has new stone formation detected on imaging during the last 5 years. Symptomatic stone defined as any of the following:
 - a. Stone passage
 - b. Procedural intervention
 - c. Radiographically or ultrasonographically confirmed stone with any of the following:
 - i. Gross hematuria
 - ii. Renal colic or atypical abdominal pain attributed to the stone, as determined by a treating provider
 - iii. A clinical pattern of intermittent symptoms consistent with intermittent obstruction at the ureteropelvic junction, as determined by a treating provider
3. Low 24-hr urine volume
 - a. ≥18 years old: <2.0 L/day
 - b. <18 years old and weight <75kg: <25 ml/Kg/day (adolescents ≥75 kg will follow the 2.0L criteria)
4. Able to provide informed consent (parental permission for children)
5. Owning and willing to use a smartphone or other device (e.g., tablet) compatible with the study-provided wireless enabled “smart” water bottle

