8.1.1 DEFINITION OF ADVERSE EVENTS (AE)

Adverse Event

An adverse event (AE) is any untoward medical occurrence associated with the use of a study intervention in a study participant. An AE can, therefore, be any unfavorable and unintended sign (including an abnormal laboratory finding, for example), symptom, or disease temporally associated with the use of a pharmaceutical product or biologic. Diseases, signs, symptoms, or laboratory abnormalities already existing at the time of consent are not considered AEs unless they worsen (i.e., increase in intensity or frequency). Surgical procedures themselves are not AEs; they are therapeutic measures for conditions that require surgery. The condition for which the surgery is required may be an AE. Surgical procedures planned before randomization and the conditions leading to these measures are not AEs.

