10.4.2 ANALYSIS OF THE PRIMARY EFFICACY ENDPOINT(S)

The primary endpoint (symptomatic stone event) will be analyzed as a time-to-event outcome with a log-rank test⁴² or equivalently, the Cox proportional hazards model,⁴³ the approach used for calculating sample size requirements. Kaplan-Meier estimates⁴⁴ of cumulative event rates as a function of follow-up time will be calculated and displayed. In addition, stratified Cox proportional hazards model will be conducted where the strata are those used in the randomization scheme. Furthermore, data collected on subsequent recurrent events of symptomatic stone will be analyzed using the Andersen-Gill model⁴⁵ (with adjustment for correlation within a study participant) and/or negative binomial regression.

A symptomatic stone event will be defined as stone passage, symptomatic stone requiring procedural intervention, or any asymptomatic stone undergoing procedural intervention. A pre-specified sensitivity analysis of the definition of symptomatic stone event will include stone passage, symptomatic stones requiring procedural intervention, and asymptomatic stones undergoing procedural intervention that meet at least one of the following criteria: stone size at least 4 mm in any dimension, mobile stone, hematuria or recurrent urinary tract infection. An additional pre-specified sensitivity analysis will exclude any symptomatic stone events that occur within 30 days of randomization.

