10.4.8 ADDITIONAL SUB-GROUP ANALYSES

Subgroup analyses will be performed for the primary outcome among the ITT population in order to explore whether intervention on symptomatic kidney stone are consistent across subgroups. The same subgroup analyses will also be repeated in the per-protocol population. Subgroups of interest would be clinical centers, sex, race, age (adult/adolescent), baseline medical treatment for USD prevention and first time/recurrent stone former. An SPS treatment fidelity subgroup analysis may be conducted, if sufficient variability in fidelity exists. Subgroup analyses will be summarized in a forest plot which will include the interaction p-values.

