10.5 SAMPLE SIZE

Conservative power calculations are based on symptomatic recurrence rates reported by Rule and colleagues.⁴⁹ The following assumptions are incorporated into the power calculation:

- 1) Unit of randomization: patient
- 2) Equal randomization ratio (1:1)
- 3) 15% event rate (composite of USD recurrence) over 2 years in control arm
- 4) 30% relative risk reduction for intervention arm (HR = 0.7)
- 5) 20% attrition rate (dropouts, loss to follow up)
- 6) Two-sided alpha of 0.05, log-rank test for time to event
- 7) 2 year follow up

$N = 821$ per arm (total = 1642 study participants) provides 80% power to detect the pre-specified relative risk. Sample size calculations were carried out using SAS (PROC POWER) version 9.4 (SAS Institute Inc., Cary, NC).

Study participants will be recruited from the 4 Clinical Centers over a 2-year period.

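### The primary endpoint counts procedures planned before randomization and events from stones already present at baseline, and no rule sets them aside

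*Combined protocol and SAP*

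**What the plan says.** Section 4.2.1 defines the endpoint as "Symptomatic kidney stone recurrence. A symptomatic stone will be defined as any of the following", followed by three components: passage seen or captured by the participant, a procedure for a symptomatic stone, and any procedure to remove an asymptomatic renal or ureteral stone. Section 10.4.2 repeats this. Neither section requires the stone to be new since baseline or the procedure to be unplanned at randomization.

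Section 5.1 asks for "At least 1 symptomatic stone event (passage or procedural intervention) within 3 years prior to enrollment", with a five-year alternative. Its item 2c also accepts an imaging-confirmed stone with symptoms, without requiring that the stone has passed or been removed. Sections 5.1 and 5.2 set no minimum time since the last event and do not exclude retained stones or booked surgery.

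For safety reporting, section 8.1.1 says: "Surgical procedures planned before randomization and the conditions leading to these measures are not AEs". Section 7.4 has a committee adjudicate procedures for whether the stone was symptomatic; adjudication of passages is not described. Section 10.4.2 adds: "An additional pre-specified sensitivity analysis will exclude any symptomatic stone events that occur within 30 days of randomization". Its other sensitivity analysis filters asymptomatic-stone procedures by size, mobility, hematuria or recurrent infection, not by whether the stone is new. Baseline stone status is not a stratification factor (section 4.3) or a listed subgroup: "Subgroups of interest would be clinical centers, sex, race, age (adult/adolescent), baseline medical treatment for USD prevention and first time/recurrent stone former". Sections 7.1.1 and 7.3 provide for baseline imaging but allow it to be waived.

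**The concern.** Consider three participants the plan would admit. One has a stone in place and a ureteroscopy booked for week 6. One had lithotripsy the month before enrollment and passes fragments at week 7. One has an asymptomatic renal stone on the baseline scan that is removed at month 3. Each becomes a primary event, and each falls outside the 30-day window.

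The first is the clearest problem: the decision preceded randomization, so no behavioral program could have averted it. The second is similar but harder to identify. The third is arguable, because fluid might affect whether a stone already present grows or needs treatment.

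Events the intervention cannot influence arise at about the same rate in both arms. If they are a material share, they move the estimated hazard ratio toward 1 and make a null result hard to interpret: it could not be separated into no effect on recurrence and an effect masked by events already set in motion.

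**Working it through.** **Inputs (section 10.5).** "Two-sided alpha of 0.05, log-rank test for time to event"; "15% event rate (composite of USD recurrence) over 2 years in control arm"; hazard ratio 0.70; 1:1 allocation; 20% attrition; N = 1642, which "provides 80% power to detect the pre-specified relative risk". The documents do not give f (the share of control-arm events from stones present at baseline) or h (the hazard ratio for those events). Both are assumptions here.

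**The plan's own figure.** Schoenfeld events = 4(1.960 + 0.842)² / (ln 0.70)² = 246.8, so 247. With two years of uniform accrual and two further years to a common close, the mean event probability is 0.186: 247 / 0.186 = 1328, and 1328 / 0.8 = 1660, within 3% of 1642. With each participant followed for a fixed 24 months, the mean probability is (0.150 + 0.1075)/2 = 0.1288: 247 / 0.1288 = 1918, and 1918 / 0.8 = 2398, which does not reproduce 1642. That is a separate matter. The illustration is therefore set at 247 events, the number that gives 80% power at 0.70.

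**Mixing the two kinds of event.** Overall HR = f·h + (1 − f)·0.70. Power = Φ(|ln HR|·√247 / 2 − 1.96). If only new-stone events are counted, the HR stays at 0.70 and events fall to 247(1 − f). With h = 1:

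| f | Overall HR | Power, all events | New-stone events | Power, new-stone only |
|---|---|---|---|---|
| 0 | 0.70 | 80% | 247 | 80% |
| 10% | 0.73 | 70% | 222 | 76% |
| 20% | 0.76 | 58% | 198 | 71% |
| 30% | 0.79 | 46% | 173 | 65% |
| 40% | 0.82 | 34% | 148 | 58% |

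So with h = 1, restricting to new stones recovers 6 to 24 points, not the whole loss.

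**Dependence on h, at f = 30%** (new-stone only: 65%):

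| h | Overall HR | Power, all events |
|---|---|---|
| 0.70 | 0.70 | 80% |
| 0.80 | 0.73 | 70% |
| 0.85 | 0.745 | 64% |
| 1.00 | 0.79 | 46% |
| 1.30 | 0.88 | 17% |

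The two approaches break even where f·h + (1 − f)·0.70 = 0.70^√(1 − f), which gives h = 0.83 at f = 10% and 0.85 at f = 40%. Below that, excluding baseline-stone events loses power; at h of 0.70 or lower there is no dilution.

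**The 30-day window.** With a constant hazard λ = −ln(0.85)/24 per month, the share of two-year control events by month m is (1 − e^(−λm))/0.15: 4.5% at month 1, 13.4% at month 3, 26.5% at month 6. This describes events in general. Booked procedures and residual fragments would cluster early, so it does not show what share of those the window removes.

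**The case against.** The strongest reply is that new-stone formation is not the primary question. Section 3 words the primary hypothesis as fewer symptomatic stones over two years, the protocol summary and section 10.4.2 speak of a symptomatic stone event, and new asymptomatic stones and growth of existing stones have their own secondary hypotheses. Counting clinical events whatever the age of the stone is defensible in a trial with pragmatic features. Secondary hypothesis 3 also expects fluid to slow growth of existing stones, so later events from them may be modifiable. This stands, and it is why such events should remain in the primary endpoint. It does not cover a procedure already decided before randomization.

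A reader might infer that the definition necessarily pulls the hazard ratio toward 1, or that the trial is underpowered by the amounts tabulated. The documents support neither. They give no f or h, and section 10.5 does not say that 0.70 refers to new stones only. Section 2.2 cites a relative risk of 0.45 for stone formation; treated as a hazard ratio, with f = 45% and h = 1, it gives 0.45 + 0.55 × 0.45 = 0.70. The planned effect may therefore already allow for such events.

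Other points stand in part. The size and mobility sensitivity analysis and the adjudication of procedures bear on some of these events, though not on stone age. The parenthesis in the lead sentence of inclusion criterion 2 sits uneasily with item 2c, so a retained qualifying stone rests on 2c being applied as written. The adverse-event rule in section 8.1.1 serves safety reporting; it does not prove an endpoint error, but it shows that pre-planned surgery was foreseen. Finally, section 10.1 places the full SAP in a separate document, which may hold a rule.

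**Conclusion.** The definitional gap holds: as written, any passage or stone procedure after randomization is a primary event, including procedures already planned or staged and events from stones present at baseline. The 30-day exclusion does not alter the primary analysis.

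For procedures fixed before randomization, the intervention cannot prevent the event, so counting them can dilute the hazard ratio. For other baseline-stone events neither the direction nor the size is established. The drop in power from 80% to between 70% and 34% is an illustration resting on three assumptions: h = 1, f between 10% and 40%, and a new-stone hazard ratio of 0.70. With h near 0.85 or below, removing those events gains little or costs power. This supports a narrow change to the primary definition and a supportive analysis for the rest, as an inexpensive improvement. It rests on the available text; the separate SAP, the Manual of Procedures and any adjudication rules were not available.

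**What to change.** 1. In sections 4.2.1 and 10.4.2, state that procedures planned or scheduled before randomization, and staged completion of a procedure begun before it, are not primary events. Record them in one eCRF field at baseline, before allocation is known.
2. Keep all other events in the primary endpoint. Code the stone in each event, blinded to arm, as present at baseline, new, or undeterminable (including imaging waived). Pre-specify a supportive analysis that excludes events attributable to a baseline stone or to fragments of a stone treated before randomization.
3. Add baseline stone on imaging (yes / no / not imaged) as a subgroup in section 10.4.8 and as a covariate in a supportive Cox model.

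**Cost.** Protocol and SAP wording, one baseline field and one coding field. Slightly fewer primary events will be counted. Passages would need coding that section 7.4 does not now provide for. Some stones will be undeterminable because imaging can be waived and fragments are hard to match to a scan; for that reason the stone-age distinction belongs in a supportive analysis. The rules should be fixed before unblinding.

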4.2.2 SECONDARY ENDPOINTS

1. Asymptomatic formation of new stone detected by imaging
2. Increased size of existing stone by ≥ 2 mm in any dimension detected by imaging
3. Composite outcome: symptomatic stone recurrence, asymptomatic stone formation, increase of existing stone by ≥ 2 mm in any dimension detected by imaging
4. 24 hour urine total volume
5. Costs of study interventions and treatments for USD during the follow-up period
6. Presence of lower urinary tract symptoms (Comprehensive Assessment of Self-reported Urinary Symptoms)

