3 OBJECTIVES AND PURPOSE

The primary aim of the study is to determine whether a multi-component program of behavioral interventions to increase fluid intake will result in reduced risk of stone disease progression over a 2-year period. Under this aim, the study will test the following specific hypotheses, comparing 1) intervention arm: individuals participating in a multi-component program of behavioral interventions targeting increased fluid intake (sufficient to achieve a urine output ≥ 2.5 L daily or ≥ 30 mL/kg/day for those study participants aged < 18 years and weighing < 75 kg); versus 2) control arm: individuals receiving usual care:

- a. **Primary hypothesis:** Participants in the intervention arm will have a reduced risk of symptomatic stones over 2 years.
- b. **Secondary hypothesis #1:** Participants in the intervention arm will have a reduced risk of stone disease progression (a composite outcome comprising symptomatic stone events, new asymptomatic stone on imaging, or stone growth of at least 2 mm on imaging) over 2 years.
- c. **Secondary hypothesis #2:** Participants in the intervention arm will have a reduced risk of forming new asymptomatic renal stones over 2 years.
- d. **Secondary hypothesis #3:** Fewer participants in the intervention arm will exhibit growth in existing renal stones of at least 2 mm on imaging over 2 years.
- e. **Secondary hypothesis #4:** Participants in the intervention arm will be more likely to achieve goal 24-hour urine output.
- f. **Secondary hypothesis #5:** Participants in the intervention arm will be more likely to develop lower urinary tract symptoms (LUTS).
- g. **Secondary hypothesis #6:** Greater urine output will be associated with reduced risk of stone disease progression, controlling for medication use (time updated), disease severity and clinical characteristics (e.g., body mass index).

h. **Secondary hypothesis #7:** Participants with pre-existing LUTS will be less likely to achieve 24-hour urine output goals as compared to those without pre-existing LUTS.

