7.3 SCHEDULE OF EVENTS TABLE

Procedure	Screen	Baseline	2 weeks ± 7 days	3 mos ± 30 days	6 mos ± 30 days	9 mos ± 30 days	12 mos ± 30 days	15 mos ± 30 days	18 mos ± 30 days	21 mos ± 30 days	24 mos ± 60 days
Informed Consent	X										
Email/Telephone Follow Up				X	X	X	X	X	X	X	X
Serum chemistry/eGFR	X										
Serum osmolality	X										
Hcg (urine dip)α		X									X
Randomization		X									
Provide smart water bottle*		X									
24-hour urine panel [†]	X [†]	X [†]									X
24-hour urine TV	X‡		X		X°		X°	X°			X°°
24-hour urine Cr	X‡		X		X°		X°	X°			X°°
24-hour urine osm	X‡		X		X°		X°	X°			X°°
Imagingα		X					X§				X~
Medical History	X										X
Weight and Height		X		X	X	X	X	X	X	X	X
LUTS assessment		X			X		X		X		X

* All participants are provided with a smart water bottle, but only participants randomized to the intervention arm are required to set-up the bottle and use it during the study.

†24-hour urine panel includes: calcium, creatinine, citrate, phosphorous, pH, sodium, urea nitrogen, oxalate, chloride, ammonium, magnesium, potassium, uric acid, sulfate, qualitative cystine. Qualitative cystine will only be performed for Week 2 collection. A Screening/Baseline 24 hour urine panel will only be done if the participant does not have the historical panel results needed for determining eligibility (see Section 7.1.1).

‡A single 24-hour urine sample will be collected at screening for participants without any 24-hour urine tests in the 12 months prior to the Screening visit and the central lab will run urine volume, creatinine and osmolality only on this sample. For participant with prior 24-hour urine tests but without the results listed in Section 7.1.1, a new sample will be collected at screening and the full panel will be run on this sample.

° For Months 6, 12, 18, a clinical 24 hr urine can be used in place of a new collection provided it is within the ±30 day window of that visit and it includes volume and creatinine.

°° For Month 24, a clinical 24 hr urine can be used in place of a new collection provided it is within the ±60 day window of that visit and it includes the results listed in Section 7.1.1.

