α Imaging at Baseline and Month 24, and the associated pregnancy testing for adult females, may be waived for participants enrolled from locations other than the primary Clinical Centers/sites, or who are enrolled from an existing CC and qualify but are declining participation in the study because of imaging. Adult female participants will be asked to verbally confirm that they are not pregnant or planning to become pregnant during their time in study.

§ Imaging = low dose CT (adults); renal u/s (adolescents); imaging at 12 months considered standard of care procedure and not required. SOC imaging done at any point during the participant's follow-up will be collected and entered in the EDC database.

~ For Month 24, imaging performed for clinical care can be used in place of new imaging provided it was completed within ± 60 days of the visit, and the criteria in Section 7.1.1 are met.

|| Assessment of Lower Urinary Tract Symptoms in study participants aged ≥18 years using Comprehensive Assessment of Self-Reported Urinary Symptoms (CASUS)

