10.3 ANALYSIS DATASETS

Data from all randomized study participants, regardless of whether or not they completed all protocol follow-up requirements, will be included for analysis. The analysis population will be the intent-to-treat (ITT) population. In addition, a per-protocol analysis will be performed. The analysis population for the per protocol analysis will consist of participants in the ITT population except those who have had a major protocol deviation.

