10.4.3 ANALYSIS OF THE SECONDARY ENDPOINT(S)

Secondary endpoints will include a composite outcome of symptomatic stone event, asymptomatic stone formation, or stone growth assessed at study conclusion. These outcomes will be analyzed using a logistic regression model, since asymptomatic stone formation or stone growth are subject to interval censoring (the exact occurrence time will be unknown).

24 hour urine total volume and lower urinary tract symptoms (as measured by CASUS) will be compared between intervention and control arms using t-test or Wilcoxon rank-sum test, based on the assumption of normality of the data.

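### The LUTS outcome is stated in three ways that do not match, so the planned test does not answer hypothesis #5 and leaves the baseline CASUS unused

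*Combined protocol and SAP*

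**What the plan says.** Three places describe the LUTS outcome.

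- Section 3, secondary hypothesis #5: "Participants in the intervention arm will be more likely to develop lower urinary tract symptoms (LUTS").
- Section 4.2.2, endpoint 6: "Presence of lower urinary tract symptoms (Comprehensive Assessment of Self-reported Urinary Symptoms").
- Section 10.4.3: "lower urinary tract symptoms (as measured by CASUS) will be compared between intervention and control arms using t-test or Wilcoxon rank-sum test", the choice depending on normality.

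Other parts of the plan bear on these. Hypothesis #7 in Section 3 states: "Participants with pre-existing LUTS will be less likely to achieve 24-hour urine output goals as compared to those without pre-existing LUTS". No exclusion criterion in Section 5.2 names LUTS. The row "LUTS assessment" in the Section 7.3 schedule is marked at baseline and at months 6, 12, 18 and 24. CASUS is given only to adults (Sections 7.1.1 and 7.3). Section 10.3 sets the general population: "The analysis population will be the intent-to-treat (ITT) population". Section 10.4.9 leaves secondary comparisons unadjusted for multiplicity.

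**The concern.** To develop LUTS, a person must be free of them at entry. Presence of LUTS is met by anyone who has them at the time of asking, including someone whose symptoms are unchanged since before randomization. A comparison of CASUS scores is a third question, about average symptom burden. These are different estimands and can give different answers in the same trial.

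LUTS is a burden that the protocol itself predicts from higher fluid intake. The safety analysis in Section 10.4.4 covers only symptomatic hyponatremia, and under Section 8.4.1 non-serious adverse events are not entered on the safety page of the eCRF. CASUS is therefore the only planned between-arm look at this burden. If its definition stays open, the trial may lack precision on a predicted harm, and the choice among three outcomes could be made after the data are seen, with no multiplicity control.

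**Working it through.** The plan gives no LUTS rate, CASUS standard deviation, or power figure for this comparison, so there is no stated figure to reproduce. The check is a comparison of texts, followed by two illustrations.

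**1. The three statements side by side**

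| | Hypothesis #5 | Endpoint 6 | Section 10.4.3 |
|---|---|---|---|
| Quantity | New LUTS | Current LUTS | CASUS compared as a score |
| Scale | Yes/no | Yes/no | Continuous or ordinal |
| Who can contribute | Those without LUTS at entry | Everyone assessed | Everyone assessed |
| Role of baseline CASUS | Essential | None stated | None stated |
| Cut-off | Needed, not given | Needed, not given | Not needed |
| Time point | Over follow-up, by implication | Not given | Not given |

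No other section reconciles them. A t-test or rank-sum test on follow-up CASUS estimates neither the risk of new LUTS nor the proportion with LUTS.

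**2. Cost of ignoring baseline in the score comparison**

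With baseline/follow-up correlation r (assumed; not in the documents) and a common slope in both arms, ANCOVA multiplies the variance of the arm difference by 1 − r².

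- r = 0.4: 1 − 0.16 = 0.84, a 16% reduction.
- r = 0.7: 1 − 0.49 = 0.51, a 49% reduction.

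**3. If presence were analysed as yes/no (an analysis the plan does not specify)**

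Let b be the share of adults with LUTS at entry, s the share of those who still have it at follow-up, and i the risk of new LUTS in the rest. The proportion with LUTS is b·s + (1 − b)·i. If s is equal in both arms, the risk difference is (1 − b) times the difference in new LUTS.

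Assumptions, none of them from the documents: 90% adults, i = 15% control and 22.5% intervention (risk ratio 1.50), s = 85% in both arms. From Section 10.5: 821 per arm and 20% attrition. This gives 821 × 0.8 × 0.9 ≈ 591 adults per arm. Power is by normal approximation for two proportions, two-sided 0.05. The new-LUTS analysis uses 591 × (1 − b) per arm.

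| b | Presence, control v intervention | Risk ratio | Power, presence | Power, new LUTS only |
|---|---|---|---|---|
| 10% | 22.0% v 28.75% | 1.31 | 76% | 88% |
| 20% | 29.0% v 35.0% | 1.21 | 60% | 84% |
| 40% | 43.0% v 47.5% | 1.10 | 34% | 73% |
| 60% | 57.0% v 60.0% | 1.05 | 18% | about 55% |

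**4. Sensitivity to equal persistence**

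Now let s be 80% in control and 90% in intervention, with everything else unchanged. At b = 20%, presence is 0.2 × 0.80 + 0.8 × 0.15 = 28.0% v 0.2 × 0.90 + 0.8 × 0.225 = 36.0%. Power for presence at b = 20%, 40% and 60% becomes 84%, 84% and 88%, against 84%, 73% and about 55% for new LUTS only. The loss disappears at 20% and reverses at 40% and 60%.

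**The case against.** A reader might infer that adults with LUTS at entry count as events and so hide a harm. The documents do not support that. Nothing in them defines a LUTS event, sets a CASUS cut-off, or plans a comparison of LUTS proportions. In the score comparison of Section 10.4.3 nobody is an event, and there is no risk ratio to pull towards 1. The dilution in step 3 applies only if endpoint 6 were analysed as yes/no. Even then it needs the program to leave persistence unchanged in those already affected, and step 4 shows how much rests on that. Nor need pre-existing cases be most of the total: in step 3 with b = 10% they are 0.085/0.22 = 39% of control-arm cases.

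Two further defences stand. Symptom burden in all randomized adults is a legitimate estimand, and randomization balances baseline LUTS in expectation, so the unadjusted comparison is valid, only less precise. A reader might also infer that adolescents would be handled as missing data. Sections 7.1.1 and 7.3 make CASUS adults-only, and Section 7.1.1 keeps participants who turn 18 on the adolescent procedures without the LUTS questionnaire.

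Finally, Section 10.1 defers full methods to a separate SAP, which may settle the definition. That does not remove the mismatch among the hypothesis, the endpoint and the analysis in the text reviewed here.

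**Conclusion.** The mismatch is real and unresolved. The planned test answers neither hypothesis #5 nor endpoint 6 as worded, and it leaves unused a baseline measurement that the trial already collects. The consequence is lost precision and an open choice of outcome. It is not a bias, and no hidden harm has been shown.

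The size is uncertain. The 16% to 49% variance reduction rests on an assumed correlation of 0.4 to 0.7. The power figures are illustrations that depend on assumed LUTS rates and on equal persistence in both arms, and should not be read as the trial's power. LUTS is one secondary endpoint, outside both the safety analysis and the sample-size basis, so the point is worth correcting but does not threaten the primary result.

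**What to change.** Make Sections 3, 4.2.2 and 10.4.3 describe the same outcomes.

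1. In Section 10.4.3, compare follow-up CASUS between arms in all participants aged 18 or over at enrollment, adjusted for baseline CASUS, for example by ANCOVA at a named visit or a mixed model over months 6, 12, 18 and 24.
2. To answer hypothesis #5, add a comparison of new LUTS among adults without LUTS on baseline CASUS, reported as risk difference and risk ratio with 95% confidence intervals. Pre-specify one CASUS cut-off for both baseline and follow-up. State either a single time point or a method that allows for missed questionnaires, because a rule counting LUTS at any visit depends on how many questionnaires each person completes. The same cut-off would define pre-existing LUTS for hypothesis #7.
3. Reword endpoint 6 to name these two outcomes.

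No new data are needed. The cost is agreeing a cut-off before unblinding and running one more analysis. The new-LUTS comparison leaves out adults with LUTS at entry, but the adjusted all-adult analysis covers them. Because the restriction uses a pre-randomization measurement, the arms remain comparable.
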